### *Auditory Perceptual Analysis*

3 blinded raters (tbd) will listen to the sentence “we were away a year ago” and rate on 100mm VAS in REDCap. The initial and final evaluations will be rated, for a total of 2 samples per participant x 28 participants = 56 samples.

Raters will be paid \$20/hour for ratings. Ratings should take in total 2 hour-long sessions.

### **Participant Payment**

Participants will be compensated \$100 in total, \$10 for the initial intake measurements, \$10 for each therapy session attended, and \$50 for the 1-week follow-up after therapy is completed.

## Safety

### *Adverse Events*

An interim analysis will be conducted at the midpoint of the study to ensure that PhoRTE+EMST is safe. During the study, each participant will be asked if they perceive their treatment to be harmful to them. If participants evince a VHI-10 increase of greater than 5 points *in addition to* reporting that voice therapy is harmful, then the study will be paused, re-evaluated, and possibly terminated. The study statistician ([name]) will perform this interim analysis: clinical investigators will remain blinded to the results in order to avoid bias. Clinical investigators will only be informed of results if there is a substantial safety concern by the midpoint of the study.

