### *VHI-10*

The primary outcome is the Voice Handicap Index-10 (VHI-10) score. The VHI-10 is a patient-centered outcome that quantifies a patient's perception of handicap caused by a voice disorder and will be measured at every session. VHI-10 will be anchored to baseline VHI-10 score (each item anchored) for the 1 week follow-up (will be administered without anchoring). Secondary outcomes include the following:

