### *Inclusion/Exclusion*

Age 65 years or older with chief complaint of a voice problem with VHI-10  $\geq 1$ . Primary diagnosis of vocal fold atrophy only as determined by a multi-disciplinary team of fellowship-trained laryngologist and voice-specialized speech-language pathologist, and willingness to be randomized to treatment option. No concomitant laryngeal diagnoses or diseases known to affect voice function, including: amyloidosis, arytenoid dislocation, laryngeal cancer, cricoarytenoid fixation, vocal fold cyst(s), vocal nodules, vocal fold polyp(s), dysplasia, vocal fold fibrous mass(es), glottal web, vocal fold immobility, laryngeal stenosis, laryngocele, leukoplakia,

Parkinson’s disease, Reinke’s edema, respiratory recurrent pneumonia, sarcoidosis, spasmodic dysphonia; any chronic lower airway disease such as chronic obstructive pulmonary disease (COPD), asthma, chronic bronchitis, emphysema, cystic fibrosis; history of acute stroke, untreated hypertension, or untreated gastroesophageal reflux disease (GERD).

*Consent*

A trained study team member will be responsible for recruiting patients. On the day of their first visit, the informed consent will be obtained. The informed consent process will occur in a private room before starting any therapy. The participants will be randomized to either of the study arms, if they consent.

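### The only explicit pause rule requires a VHI-10 rise above 5 points as well as a harm report, so it cannot respond to EMST harm that leaves VHI-10 within 5 points, although the interim is meant to secure the safety of PhoRTE+EMST

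*Combined protocol and SAP*

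**What the plan says.** All the safety provisions are in one paragraph of the combined protocol and SAP, under Safety, Adverse Events. It has four elements.

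- **Purpose.** "An interim analysis will be conducted at the midpoint of the study to ensure that PhoRTE+EMST is safe".
- **Question.** During the study, "each participant will be asked if they perceive their treatment to be harmful to them".
- **Pause rule.** It has two conditions, joined by an emphasised phrase meaning that both are needed: "If participants evince a VHI-10 increase of greater than 5 points", and the participant "reporting that voice therapy is harmful, then the study will be paused", with re-evaluation and possible termination to follow.
- **Disclosure.** The statistician performs the interim analysis and the clinical investigators stay blinded to it. "Clinical investigators will only be informed of results if there is a substantial safety concern by the midpoint of the study".

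Other sections bear on how this paragraph works. The VHI-10 section says that the score "quantifies a patient's perception of handicap caused by a voice disorder and will be measured at every session". The EMST Training section describes a device that progressively strengthens the respiratory muscles, and Outline of Procedures gives it to one arm only. Data Entry lists maximum expiratory pressure, VHI-10 and practice logs for each session, with no item for the harm question or for adverse events. The Data Analysis Plan contains no safety analysis.

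**The concern.** The purpose, the question and the trigger differ in scope. The purpose concerns the combination of PhoRTE and EMST. The question concerns whatever treatment the participant receives. The trigger concerns voice therapy, and only where perceived voice handicap has also risen by more than 5 points.

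EMST is the only component that differs between the arms, so it is the component on which a safety interim has most to say. It loads the respiratory muscles, whereas VHI-10 scores handicap from a voice disorder. A participant could report harm from the device while VHI-10 stays the same, improves, or rises by 5 points or less. Under the rule as written, that report does not count towards a pause. If an untriggered rule were then taken as evidence that the combination is safe, the conclusion would go further than the rule can support.

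**Working it through.** **1. The rule as a logical condition.** Let A be a VHI-10 rise above 5 points and B a report that voice therapy is harmful. The rule is A and B. If A is false, the rule is not met, whatever B is and however many participants report harm. Reading voice therapy broadly, so that EMST harm satisfies B, does not change this, because A still has to hold.

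**2. Other routes in the text.** The paragraph gives one: investigators are told if there is a substantial safety concern. The term is not defined, it is not confined to the VHI-10 trigger, and its only stated consequence is that investigators are informed. No other section defines, grades or schedules the collection of adverse events.

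**3. Illustration.** The documents give no operating characteristic for the rule, so there is no figure to reproduce. Let q be the proportion of EMST participants who perceive harm, s the share of those whose VHI-10 rises by more than 5, and n the number of EMST participants observed. Then

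P(at least one participant meets the rule) = 1 − (1 − q·s)^n.

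Take n = 7, that is 28 ÷ 2 = 14 at the midpoint and 14 ÷ 2 = 7 per arm. Both q and s are assumed. The formula also assumes that one participant is enough and that EMST harm is accepted as B.

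| s | q = 5% | q = 10% | q = 20% |
|---|---|---|---|
| 0 | 0% | 0% | 0% |
| 25% | 8% | 16% | 30% |
| 50% | 16% | 30% | 52% |
| 100% | 30% | 52% | 79% |

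For example, q = 10% and s = 25% give 1 − 0.975^7 = 0.162. The first row restates step 1. The other rows show how strongly the rule depends on s, which the documents do not give.

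**4. What the sample can exclude.** With zero events in n participants, the exact one-sided 95% upper bound on the event rate is 1 − 0.05^(1/n).

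- Midpoint, n = 7: 1 − 0.05^(1/7) = 0.348, or 35%. The upper limit of the two-sided 95% interval is 1 − 0.025^(1/7) = 0.410, or 41%.
- End of study, n = 14 (the Participants section gives 14 per arm): 1 − 0.05^(1/14) = 0.193, or 19%.

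These bounds concern sample size and would apply under any trigger. They bear on the word *ensure*, separately from step 1.

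**The case against.** The best defence is that the pause rule is not the whole of the safety provision. Every participant is asked about harm, the statistician reviews results at the midpoint, and a substantial safety concern goes to the investigators. This stands in part. A reader might infer that the interim would look reassuring at any rate of EMST harm, and the text does not support that, because this second route could carry such harm. It has no definition and no pause attached, however, so the gap in the pause rule remains.

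Some further readings are tempting, and the documents do not bear them out.

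- **Voice therapy against treatment as a flat contradiction.** Outline of Procedures describes four sessions of voice therapy, and its table shows PhoRTE with or without EMST in each, so the term can be read to cover both. The wording is loose, and the point does not depend on it.
- **The exclusion criteria as evidence that the sponsor had non-voice risks in mind.** The list ends with "history of acute stroke, untreated hypertension, or untreated gastroesophageal reflux disease (GERD", but it opens as a list of laryngeal diagnoses and diseases that affect the voice, and no safety reason is stated.
- **A conflict of timing that leaves the second half of the study without review.** The pause sentence has no time limit and VHI-10 is taken at every session, so the rule can be read as running throughout, alongside a separate midpoint analysis. This is an ambiguity.
- **A particular share of harm reports being disregarded.** The documents give no basis for one, and nowhere say that reports are to be set aside.
- **Safety as an aim of the trial.** It is the purpose of the interim. The trial's primary objective is additional benefit, and no safety conclusion is stated in advance.

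**Conclusion.** The point holds as a defect in a stated rule. Followed exactly, the only explicit pause rule cannot be met by a harm report without a VHI-10 rise above 5 points. This follows from the wording alone and needs no outside figure. It is a statement about the pause rule, not about everything the statistician might notice or pass on.

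The purpose given to the interim also exceeds what the numbers allow. With no events at all, a true rate of up to 35% in the EMST arm is compatible with the midpoint data, and up to 19% with the final data (one-sided 95%). The 35% assumes that the midpoint means half of 28 participants with equal allocation, which the section does not define. The 19% assumes that all 14 are observed. The illustrative trigger probabilities rest on assumed inputs, and the conclusion does not rest on them.

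This is a change the sponsor should make. It does not touch the efficacy comparison.

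**What to change.** **Reconcile the paragraph.** The sponsor and clinical team should bring the interim purpose, the harm question and the pause trigger into agreement. They should state whether the trigger applies throughout or only at the midpoint, and define the midpoint and what counts as a substantial safety concern. The choice of rule is theirs; none is proposed here.

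**Add a safety analysis to the Data Analysis Plan.** Suggested text: *At the interim and at study end, the number and proportion of participants in each arm who report harm in answer to the harm question, and who have any reported adverse event, will be tabulated with exact binomial confidence intervals, irrespective of the change in VHI-10.* The interim table would stay with the statistician, in line with the blinding already described.

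**Record the answer.** Add the harm question to the REDCap session items, since Data Entry lists no field for it.

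**Replace the claim of ensuring safety** with the event rate that the sample can exclude, using the bounds above or their equivalent for the actual number observed.

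**Cost.** One reworded paragraph, one table by arm and possibly one data field. The downside is a less favourable safety statement. Because no general adverse-event collection is scheduled, the table will be complete only for the harm question; other events will appear only if they happen to be reported.

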### *Fidelity Checks*

Each therapy session will be video-taped for future fidelity checks by the PI. These checks will ensure SLP accuracy in delivering CTT skill instructions, homework instructions, and maintaining conversation as the sole therapeutic stimulus. The review will occur after session 2 and 4 so that the PI can provide feedback to the SLP.

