**Intervention/Experimental Protocol**

*Outline Of Procedures*

The experimental protocol consists of pre-treatment and post-treatment acoustic and aerodynamic data collection and four 45-minute sessions of voice therapy. All subjects will complete PhoRTE therapy, and those in the EMST+PhoRTE arm in the study will also undergo EMST training. Before each PhoRTE therapy, subjects will report to the PI so that therapists are blinded as to which treatment group each subject is in.

Baseline	Therapy 1	Therapy 2	Therapy 3	Therapy 4	Post-Tx
Pre-Tx Acoustic and Aerodynamic Measurements, VHI-10, AVI, MEP	PhoRTE +/- EMST  VHI-10 MEP	PhoRTE +/- EMST  VHI-10 MEP	PhoRTE +/- EMST  VHI-10 MEP	PhoRTE +/- EMST  VHI-10 MEP	Acoustic and Aerodynamic Measurements, VHI-10, AVI, MEP

*PhoRTE Therapy (Standard of Care Treatment)*

Each therapy session will last for 45 minutes.

1st PhoRTE treatment session

- Check in with your patient about current status
  - o Do you have any questions since we last met? Do you have any concerns about your ability to commit to PhoRTE?
- Check in with the patient to verify implementation of voice care program
  - o Dehydration, non-phonatory inflammation (reflux, illness)
  - o Phonotrauma (throat clearing, cough)
  - o Caffeine
- Provide patients with PhoRTE therapy information sheets, phrase list, and practice sheets
- Set up the patient for home practice
  - o Verify that patient is able to download a decibel meter app successfully, and configure the app’s settings with a sound pressure level meter for home practice

- Orient the patient to the app; teach them how to open and utilize the app for home practice; demonstrate for the patient how to standardize mic-to-mouth distance
- Verify that 10 functional phrases for practice are written. Review phrases for length and that they are representative of typical communication
- Teaching proper breathing form
  - Establish efficient respiratory mechanisms to effectively execute PhoRTE exercises
  - Ex. "Place your hand on your upper abdomen just above your belly button. Now, I want you to sustain the sound "sh" for as long as is comfortable. Notice the inward movement of your hand as you exhale and sustain "sh." Let's practice this breathing a few more times until you feel comfortable with this task."

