### *Data Entry*

At the start of each therapy session, the study coordinator (PI or Co-I if study coordinator is not available) will have the participant sit in the Voice Research Lab and complete the following outcomes:

- MEP measurement through the manometer
- Complete VHI-10 in REDCap

The study coordinator will enter the following data into REDCap:

- Weekly practice logs for PhoRTE and/or EMST

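### The PI, who by implication knows each participant's arm, gives the blinded therapists mid-course feedback with no arm-blind review: a possible route for performance bias

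*Combined protocol and SAP*

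**What the plan says.** **Treatment contrast (Outline Of Procedures).** EMST is the only planned difference between the arms: "All subjects will complete PhoRTE therapy, and those in the EMST+PhoRTE arm in the study will also undergo EMST training". The course is "four 45-minute sessions of voice therapy".

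**Therapist blinding (same section).** Before each PhoRTE session, "subjects will report to the PI so that therapists are blinded as to which treatment group each subject is in".

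**Fidelity review (Safety, Fidelity Checks).** "Each therapy session will be video-taped for future fidelity checks by the PI". On timing and purpose: "The review will occur after session 2 and 4 so that the PI can provide feedback to the SLP". On content: "These checks will ensure SLP accuracy in delivering CTT skill instructions, homework instructions, and maintaining conversation as the sole therapeutic stimulus".

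**Pre-session measurement (Data Entry).** MEP and VHI-10 are collected by someone who may or may not be the PI: "the study coordinator (PI or Co-I if study coordinator is not available) will have the participant sit in the Voice Research Lab". The coordinator also enters the weekly practice logs, including those for EMST.

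**Other blinding.** Under Adverse Events, "clinical investigators will remain blinded to the results in order to avoid bias". That refers to the interim results, not to treatment assignment. The three blinded raters under Auditory Perceptual Analysis judge voice recordings, not therapy sessions.

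**The concern.** The trial asks what EMST adds to PhoRTE. The arm difference answers that only if PhoRTE is delivered alike in both arms. The protocol does not say this in so many words, but it follows from the add-on design and explains why the therapists are blinded.

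The plan puts the PI between participant and therapist to protect that blinding, then has the PI watch the therapist's sessions and coach the therapist. If the PI knows the arm, the feedback could differ by arm without anyone intending it, or could let the therapist guess the arm. Either would change PhoRTE after randomisation. The planned t-test compares arm means and cannot separate arm-dependent coaching from an effect of EMST. The primary outcome, VHI-10, is patient-reported and is collected at every session and at follow-up, so it includes measurements taken after the coaching.

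**Working it through.** The plan gives no figure to reproduce. The check is a cross-reading of the sections, followed by a count of the sessions exposed.

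**Step 1. Does the PI know the arm?** Outline Of Procedures names the PI and gives therapist blinding as the reason for the visit. The visit serves that purpose if the arm-specific step takes place there, out of the therapist's sight, so knowledge of arm is the natural inference. It remains an inference, for three reasons:
- The section does not say what the PI does at the visit.
- Both arms attend, and the schedule lists MEP for both.
- Data Entry gives pre-session MEP to the coordinator, with the PI or a Co-I as back-up only. The pre-session list that includes EMST calibration names nobody.

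**Step 2. Can the PI influence delivery?** Yes. Fidelity Checks gives feedback to the therapist as the purpose of the review.

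**Step 3. When?** The course has four sessions. Feedback after session 2 can alter sessions 3 and 4 of the same participant. Feedback after session 4 comes too late for that participant but can alter delivery to later ones.

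**Step 4. Is there a safeguard?** No section provides for review without knowledge of arm, a separate reviewer, or scripted feedback. The stated criteria (CTT and conversation as the only stimulus) do not describe the PhoRTE exercises, so they set no usable bounds on feedback about PhoRTE.

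**Step 5. Sessions exposed to feedback after session 2.** Inputs: 28 participants, 14 per arm (Participants); 4 sessions each (Outline Of Procedures).
- All sessions: 28 × 4 = 112.
- Sessions 3 and 4: 28 × 2 = 56.
- Share: 56 / 112 = 50%.

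This is an upper bound. It assumes that every participant's session 2 is reviewed, that feedback arrives before session 3, and that nobody drops out.

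**Step 6. How a shift would enter the result.** If coaching moved VHI-10 by d points in k of the 14 participants of one arm and in none of the other, the arm difference would move by k × d / 14. With k = 14 that is d; with k = 7 it is d / 2. The documents give no basis for a value of d or its sign.

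**The case against.** **The PI's role is not spelled out.** A reader might infer that the PI delivers or sets the EMST training. The documents do not say so, and Data Entry points to the coordinator for at least the MEP measurement. This objection stands: the claim has to rest on implied knowledge of arm. It does not remove the point, because Outline Of Procedures still names the PI and gives blinding as the reason.

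**Fidelity feedback normally makes delivery more uniform, and the therapy is scripted.** The protocol gives clinician wording for each exercise and a rule for the starting intensity target, which narrows the room for drift. That is fair as far as it goes. But the criteria in Fidelity Checks are not tied to those scripts, so the scripts do not limit what the feedback may cover.

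**The exposure count is generous.** Fidelity Checks does not say explicitly that every participant's sessions are reviewed. Study design and Methods adds a second recruiting centre under its own IRB, and the reviewer there is not stated. Both objections stand, so 56 is a ceiling and not an estimate.

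**Delivery can be checked afterwards.** All sessions are to be taped, so a rater unaware of arm could later compare PhoRTE delivery between arms. That could detect unequal delivery. It could not undo its effect on VHI-10.

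**The more certain fault in Fidelity Checks is the CTT wording.** Agreed: as written, the check does not describe this trial's therapy and would not verify equal PhoRTE delivery. It is a separate defect, best corrected in the same edit.

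**Conclusion.** The point holds as a gap in role separation. The plan blinds therapists by routing participants through the PI, then has the PI coach those therapists, with no provision for arm-blind review or limited feedback. This weakens a safeguard that the plan itself sets up and leaves open a route for performance bias.

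Its extent is at most 56 of 112 sessions through feedback after session 2, under the assumptions listed, plus an uncounted carry-over to later participants from feedback after session 4. The size and direction of any effect on VHI-10 cannot be estimated. The conclusion rests on one inference, that the PI knows the arm.

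A reader might go further and conclude that the arm comparison will be biased or that the therapists are in effect unblinded. The documents do not support either: they show a possible route, not that feedback would differ by arm or disclose it. The change is worth making because it is cheap and must be made before sessions are delivered.

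**What to change.** Reconcile Outline Of Procedures, Data Entry and Fidelity Checks so that whoever reviews the videos and gives feedback has no arm-specific task and no knowledge of arm. There are two workable ways:

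- **(a)** A Co-I reviews the videos and gives the feedback. Data Entry now names the Co-I as back-up for MEP, so that role must be removed for this person.
- **(b)** The coordinator takes the whole arm-specific pre-session step, with the Co-I as the only back-up. The PI is removed from that step and from the back-up role, is kept blinded, and stays as reviewer. The coordinator already enters the EMST practice logs, so this adds no new unblinded person. The documents do not say whether the coordinator is trained to run the EMST step; that must be confirmed.

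Under either option:
- Replace the CTT and conversation criteria with a fixed list taken from the PhoRTE session outline and exercise scripts, and limit feedback to its items.
- State that the taped part of the session excludes any EMST activity, so that the video does not show the arm.
- Name the reviewer at the second centre.
- Report fidelity scores by arm.

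The cost is a swap of roles among existing staff, edits to three sections, a short checklist to write and brief, and less flexibility in back-up cover when the coordinator is absent.

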#### Before therapy sessions

- Determine noise level in treatment room
- Position sound level meter 12 inches from patient's mouth
- Sustain /a/ at modal pitch and comfortable loudness; have patient use speaking voice in two takes – Rainbow Passage and monologue of 30-60 sec
- Calculate the patient's vocal intensity range (i.e. maximum dB SPL minus minimum dB SPL)
- The starting PhoRTE vocal exercise target is 50-60% of dynamic range, and add dB SPL amount to average vocal intensity of monologue
- Complete EMST calibration and MEP measurement (see description below)

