#### Exercise 1 – Phonation-Respiratory Isotonics (PhoRTE-ISO)

- Clinician: "Place your hand on your upper abdomen. Now, I want you to sustain the sound "ah" with a strong, energized voice for as long as your are able. Your starting vocal intensity is \_\_\_\_dB. You will need to achieve your target vocal intensity and maintain it during the entire "ah" to get maximal benefit from this PhoRTE exercise. I want you to check that your mouth is at the appropriate distance from the app. Let's practice this first PhoRTE exercise a few times until you feel comfortable with the task. Remember to record on your PhoRTE log the length of time you are able to hold each "ah."

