### Exercise 2 – Eccentric-Concentric Cricothyroid Contraction (PhoRTE-EC)

- Clinician: “Just like stretching exercises are good for your arms and legs to keep you young and flexible, first we are going to produce an ascending and descending pitch glide with a strong, energized voice without strain. Place your hand back on your upper abdomen. Again, your starting target vocal intensity is \_\_\_\_dB. You will need to achieve your target intensity and maintain it during the entire pitch glide. If you have difficulties achieving a strong, energized voice at the low end of your range, don’t worry. That’s typical. After completing five ascending-descending glides, then reverse and produce five descending-ascending glides with a strong, energized voice without strain.”

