### Exercise 3 – Phonation-Respiratory Power Endurance (PhoRTE-PE)

- Exercise A → functional phrases in a higher, energized calling voice
  - o Clinician: “Place your hand back on your upper abdomen. Again, your starting target vocal intensity is \_\_\_\_dB. You will need to achieve your target intensity and maintain it during the production of functional phrases. The first time we are going to say the phrases in a higher pitch with an energized voice as if we are calling to our neighbor by throwing your voice.” (Clinician demonstrates megaphone gesture with hands around mouth). Breathe as you feel necessary but avoid overtly large breaths before each subsequent
- Exercise B → functional phrases in a lower, energized voice of authority
  - o Clinician: “Place your hand back on your upper abdomen. Again, your starting target vocal intensity is \_\_\_\_dB. You will need to achieve your target intensity and maintain it during the production of functional phrases. This time we are going to say them in a lower pitch with an energized voice of authority. Breathe as you feel necessary but avoid overly large breaths before each subsequent sentence.”
- Tips to the clinician
  - o Start at resting expiratory level (the point in the breathing cycle at the end of quiet expiration). Beware they are not breath holding or using a strained/pressed production. The goal is for the patient to increase muscle activity of the abdominal musculature rather than over-utilizing/straining laryngeal musculature. Encourage the patient to, at most, take a small replenishing breath between each phrase.
  - o Natural variability in vocal intensity around the target dB will exist due to differences in speech sound sonority and linguistic stress patterns.
  - o Some patients have more difficulty with the voice of authority (vs. the calling voice). This difficulty may be due to a number of sources: (1) the positive nature of the phrase does not lend itself to a voice of authority, for example, “I love you; (2) structurally, the nature of presbyphonia results in patients using laryngeal compensation to achieve better vocal fold closure, which leads to a higher pitch; (3) some people’s personality or past experiences makes it uncomfortable for the patient to produce a voice of authority. The key for patients is to remember that this manner of production promotes the natural

pitch variability in conversation, and is not meant to conjure up negative feelings or emotions.

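### The fidelity check asks for conversation-only therapy and uses an undefined term, CTT, but the therapy scripted for both arms is PhoRTE

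*Combined protocol and SAP*

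**What the plan says.** Fidelity Checks, under Safety in the combined protocol and SAP, has every therapy session video-taped. The PI reviews after sessions 2 and 4 and gives feedback to the speech-language pathologist (SLP). The content of the review is one sentence: "These checks will ensure SLP accuracy in delivering CTT skill instructions, homework instructions, and maintaining conversation as the sole therapeutic stimulus".

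The study therapy is set out under Intervention/Experimental Protocol: "All subjects will complete PhoRTE therapy, and those in the EMST+PhoRTE arm in the study will also undergo EMST training". That section adds: "Before each PhoRTE therapy, subjects will report to the PI so that therapists are blinded as to which treatment group each subject is in". What the therapist delivers is therefore PhoRTE, in both arms.

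PhoRTE is then scripted exercise by exercise:

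- Exercise 1 is a sustained *ah*: "You will need to achieve your target vocal intensity and maintain it during the entire" vowel.
- Exercise 2 is pitch glides: "first we are going to produce an ascending and descending pitch glide with a strong, energized voice without strain".
- Exercise 3 is the participant's own list of phrases, said first at a higher and then at a lower pitch: "You will need to achieve your target intensity and maintain it during the production of functional phrases".
- Exercise 4 is speaking in a strong voice for between 30 seconds and 2 minutes.

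The first session also includes breathing practice on a sustained *sh* and an instruction to "Set up the patient for home practice".

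**The concern.** A fidelity check is meant to show that the therapy delivered is the therapy the protocol describes. Here the two descriptions differ. The check wants conversation and nothing else as the stimulus, while most of the script is not conversation. The check also names a set of skill instructions, CTT, that a rater cannot look up anywhere in the document.

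This is the only planned check on therapist delivery, and it has an operational use because the PI gives feedback from it. Each participant has four sessions, so the review after session 2 comes with half the course still to be delivered. Feedback given literally against the conversation criterion would steer a therapist away from scripted PhoRTE, which is the comparator and also the common base of both arms. A completed review would not be evidence that PhoRTE was delivered as planned.

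**Working it through.** No arithmetic beyond counting applies, and the plan gives no figure to reproduce. The check sets the three criteria in Fidelity Checks beside the rest of the document.

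**Step 1. Each criterion against the script.**

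| Criterion in Fidelity Checks | What the rest of the document gives | Result |
|---|---|---|
| Accurate CTT skill instructions | CTT occurs once, in this sentence, and is not expanded | Cannot be applied |
| Accurate homework instructions | Home practice is set up in the first session and has its own forms and information sheet | Fits |
| Conversation as the only stimulus | Exercises 1 to 3 use other stimuli | Contradicted |

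Total: 1 undefined + 1 that fits + 1 contradicted = 3 criteria.

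**Step 2. Each in-session exercise against the conversation criterion.**

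| Exercise | Stimulus | Conversation? |
|---|---|---|
| 1 (PhoRTE-ISO) | Sustained *ah* | No |
| 2 (PhoRTE-EC) | Ascending and descending glides | No |
| 3 (PhoRTE-PE) | Listed phrases in two voices | No |
| 4 (PhoRTE-ME) | 30 seconds to 2 minutes of speaking | Arguable; the script does not call it conversation |

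At least 3 of 4 exercises conflict with the criterion. The *sh* breathing practice in the first session conflicts too. Because the criterion says conversation is the sole stimulus, one exercise of another kind is enough to break it.

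**Step 3. Does another section resolve it?** Outside Fidelity Checks, conversation is mentioned once, in the clinician tips for Exercise 3, as a remark on natural pitch variability and not as a stimulus. No other section gives fidelity items for PhoRTE. The abstract, background, design and procedures all name PhoRTE, with or without EMST, and no other voice therapy. Fidelity Checks is the section out of line.

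**Step 4. What could be checked instead?** The scripts for all four exercises tell the participant a starting intensity in dB, so the therapist's statement of it is an observable act of delivery. Whether the participant holds that intensity is different. It is a decibel value, it concerns the participant's performance, and nothing in the document says that a meter reading is captured on the video. The exercises are also not assigned to particular sessions, so the document does not show which of them a given recording should contain.

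**The case against.** The strongest reply is that little turns on this. PhoRTE is scripted in detail, so the PI has a usable reference whatever Fidelity Checks says. Fidelity is not among the listed outcomes, and the Data Analysis Plan does not use it. Wanting an itemised list in a short paragraph is partly a matter of preference.

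Much of that stands. That the section names no PhoRTE exercise shows a lack of detail, not a second error, and the PI may well review against the script in practice. It does not repair the sentence, though. The written criterion remains the stated standard for feedback, and it points away from the script.

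Three stronger readings are tempting and are not supported:

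- *Correctly delivered PhoRTE would be marked as failing.* The section has no scoring rule or pass mark. The documents support only the statement that such a session cannot literally meet the criterion.
- *The comparison of the arms is biased, or VHI-10 results are affected.* Both arms receive PhoRTE, and the documents contain nothing from which such an effect could be shown or sized.
- *CTT is a different therapy, or the text was carried over from another study.* The document does not say what CTT stands for, so neither can be concluded.

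**Conclusion.** The point holds as an internal inconsistency. Of the three fidelity criteria, one is contradicted by the scripted therapy, one rests on an undefined term, and one fits. At least 3 of the 4 in-session exercises cannot be reconciled with the conversation criterion. As written, the check would give feedback against a standard that does not describe the study therapy and could not document delivery of PhoRTE.

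This assumes that sole and conversation carry their ordinary meanings, and that the exercise scripts, which agree with the rest of the document, describe the intended therapy. The consequence is confined to the fidelity check and the feedback drawn from it. It should be corrected, but it does not by itself call the primary comparison into question.

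**What to change.** Reconcile Fidelity Checks with the PhoRTE procedures and exercise scripts:

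- Keep the homework item.
- Remove the criterion that conversation be the only stimulus.
- Define CTT, or replace it with a term the document uses.
- Check therapist delivery against steps already scripted: the exercises planned for the reviewed session are instructed as scripted, and the target intensity is stated to the participant. Do not list maintained intensity as an item to be read from the video unless the sponsor confirms that the reading is recorded.
- Have the sponsor confirm which exercises belong to which session, since the scripts do not assign them.

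The cost is one reworded sentence and a short checklist. Taping of every session and PI review after sessions 2 and 4 are already planned, and no exercise or schedule changes.
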